9.5.2 Individual Halting Rules (Termination of Study Product Administration)

Study product administration may be discontinued if any of the following criteria are met:

- Any clinical adverse event (AE), intercurrent illness, or other medical condition occurs that, in the opinion of the investigator, continued receipt of study product would not be in the best interest of the subject;
- New onset of illness or condition that meets exclusion criteria
- Inadequate clinical response that requires off-study antimicrobial therapy.
 - Subjects who require off-study antimicrobial therapy will be defined as having an inadequate clinical response.

Subjects may stop study drug treatment at any time of their own volition or at the advice of their treating provider or the study investigators. Subjects who stop study product for any reason will be regarded as having withdrawn from treatment but not as having withdrawn from the study (i.e, subjects will be asked to continue to participate in follow-up visits). All subjects with an inadequate clinical response will be referred to a non-study healthcare provider for evaluation and possible treatment outside of the clinical study.

At the time of withdrawal, subjects will undergo an early termination visit if they are not willing to participate in the remaining follow-up visits

9.6 Safety Oversight

9.6.1 Data and Safety Monitoring Board (DSMB)

Safety oversight will be conducted by a DSMB that is an independent group of experts that monitors subject safety and advises DMID. The DSMB members will be separate and independent of study personnel participating in this trial and should not have scientific, financial or other conflict of interest related to the study. The DSMB will consist of members with appropriate expertise to contribute to the interpretation of the data from this trial.

The DSMB will review study progress and participant, clinical and safety data at the following time points:

- Annually at the completion of each respiratory disease season;
- Final review meeting, approximately 6-8 months after clinical database lock to review the cumulative unblinded safety and efficacy data for this trial. The data will be provided in a standard summary format;
- Ad hoc when a halting rule is met, for immediate concerns regarding observations during the study, or as needed.

The DSMB will operate under the rules of a DMID-approved charter that will be written at the organizational meeting of the DSMB. At this time, each data element that the DSMB needs to assess will be clearly defined. Procedures for DSMB reviews/meetings will be defined in the charter. The DSMB will review applicable data to include, but not limited to, study progress and participant, clinical, and safety data that may include enrollment and demographic information, medical history, concomitant medications, physical assessments, dosing, solicited events, and SAEs. Additional data may be requested by the DSMB, and interim statistical reports may be generated as deemed necessary and appropriate by DMID. The DSMB may receive data in aggregate and presented by group. The DSMB will meet and review this data at scheduled time points or ad hoc as needed during the study as defined in the DSMB charter. As an outcome of each review/meeting, the DSMB will make a recommendation as to the advisability of proceeding with study product administration, and to continue, modify, or terminate the study.

DMID, the PI, or the DSMB chair may convene the DSMB on an ad hoc basis according to protocol criteria or if there are immediate concerns regarding observations during the course of the study. The DMID Medical Monitor is empowered to stop enrollment and study treatment if the halting criteria is met or in case of any safety concern. The DMID Medical Monitor will be responsible for reviewing SAEs in real time. The DSMB will review SAEs on a regular basis and ad hoc during the study.

10 CLINICAL MONITORING

10.1 Site Monitoring Plan

Site monitoring is conducted to ensure that the human subject protections, study and laboratory procedures, study intervention administration, and data collection processes are of high quality and meet sponsor, ICH/GCP guidelines and applicable regulations, and that the study is conducted in accordance with the protocol, protocol-specific MOP and applicable sponsor standard operating procedures. DMID, the sponsoring agency, or its designee will conduct site-monitoring visits as detailed in the clinical monitoring plan.

Site visits will be made at standard intervals as defined by DMID in a separate monitoring plan and may be made more frequently as directed by DMID. Monitoring visits will include, but are not limited to, review of regulatory files, accountability records, eCRFs, informed consent forms, medical and laboratory reports, and protocol and GCP compliance. Site monitors will have access to the study site, study personnel, and all study documentation according to the DMID-approved site monitoring plan. Study monitors will meet with site principal investigators to discuss any issues noted

In this protocol, a 'specific site' is defined as one in which resources for the study (e.g., study staff, storage facilities, drug storage, or study records) are housed. Monitoring visits will focus on these specific sites to ensure compliance with DMID and ICH/GCP policies, procedures, and guidelines. In addition, a significant number of visits will occur in non-site locations, such as community clinics or home visits. These 'generic' sites will not be considered part of the site monitoring plan.

11 STATISTICAL CONSIDERATIONS

This is a randomized double-blinded placebo-controlled trial comparing a strategy of short course (5-days) vs. standard course (10-days) oral beta-lactam antibiotic therapy with respect to desirability of outcome in children with CAP.

The trial is designed using Response Adjusted for Days of Antibiotic Risk (RADAR).¹¹ RADAR utilizes a superiority trial design under the conceptual framework, evaluating whether a strategy of short course antibiotic therapy is better than the standard course strategy when considering the totality of all of the important outcomes (adequacy of the clinical response, adverse events, and the duration of antibiotic use).

All trial participants are assigned a desirability of outcome ranking (DOOR), constructed as follows:

- I. Each subject is evaluated according to the ordinal clinical response (Refer to Section 3.2.1)
- II. DOOR is assigned according to two rules:
 - (i) When comparing two subjects with different ordinal clinical responses, the subject with a better ordinal clinical response receives a higher rank.
 - (ii) When comparing two subjects with the same ordinal clinical response, the subject with fewer days of antibiotic use receives a higher rank. Days of antibiotic use are defined as the number of days for which the subject is reported to have taken at least one dose of non-placebo study product or a non-study product systemic antibiotic.

During analyses, the distributions of DOORs are compared between short-course and standard-course strategies. The sum of the probability that a randomly selected participant from the short course strategy will have a better DOOR than a randomly selected participant from the standard course strategy plus one-half the probability that the DOORs are equal is estimated using a confidence interval.

The primary outcome measure is the DOOR at Outcome Assessment Visit #1 (defined above). DOOR at Outcome Assessment Visit #1 is computed using data from Day 1 to Day 5.

Secondary outcome measures include:

1. DOOR at Outcome Assessment Visit #2.
2. Resolution of symptoms (a component of DOOR) at each outcome assessment visit, defined as the absence of fever, tachypnea, or cough of grade 2 or higher.
3. Adequate clinical response rates (a component of DOOR) at each outcome assessment visit, defined as the absence of a medically attended visit to an ED or outpatient clinic or hospitalization for persistent or worsening pneumonia that occurs after randomization and receipt of at least one dose of study drug.
4. Frequency of solicited events at each outcome assessment visit, as listed in Table 3.

-
5. Medically attended visits to ED or clinic; hospitalizations; surgical procedures; and receipt of non-study systemic antibiotics for persistent or worsening pneumonia (as defined above) at each outcome assessment visit
 - i. Individual event types (e.g., medical visits, hospitalizations, surgical procedures, and receipt of non-study systemic antibiotics) will be compared between treatment groups.
 6. Medically attended visits to ED or clinic; hospitalizations; surgical procedures; and receipt of non-study systemic antibiotics for all causes at each outcome assessment visit
 - i. Individual event types (e.g., medical visits, hospitalizations surgical procedures, and receipt of non-study systemic antibiotic) will be compared between treatment groups.

Exploratory outcome measures include:

1. DOOR at Outcome Assessment Visits #1 and #2, when increasing the threshold in assigning different ranks due to differing numbers of days of antibiotic use from a one day difference to a two, three, four, or five day difference.

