3.2 Study Outcome Measures

3.2.1 Primary Outcome Measures

The primary endpoint/outcome measure is the DOOR at Outcome Assessment Visit #1.

DOOR is defined as follows:

- I. Each subject is evaluated according to the ordinal composite outcome (See Table 1 below) and assigned an outcome rank ranging from 1-8.
- II. Desirability of Outcome Ranking (DOOR) is then assigned according to two rules:
 - (i) When comparing two subjects with different ordinal responses, the subject with a better ordinal response receives a higher rank.
 - (ii) When comparing two subjects with identical ordinal responses, the subject with fewer days of antibiotic use receives a higher rank.

The ordinal composite outcome involves an assessment of whether the subject has an adequate clinical response and whether they have experienced any solicited events as defined below.

Table 1. Ordinal Outcome

	Adequate clinical response¹ (Assessed at Outcome Assessment Visits #1 and #2)	Solicited events³ (Assessed at Outcome Assessment Visits #1 and #2)
1	Yes, with resolution of symptoms ²	None
2	Yes, with resolution of symptoms ²	Mild (Grade 1)
3	Yes, with resolution of symptoms ²	Moderate (Grade 2)
4	Yes, with resolution of symptoms ²	Severe (Grade 3)
5	Yes, with persistent symptoms of fever, tachypnea, or cough	None or any grade
6	No, with ED/clinic visit but no hospitalization	None or any grade
7	No, with hospitalization	None or any grade
8	Death from any cause	

¹Adequate clinical response is defined as the absence of a medically attended visit to an ED or outpatient clinic or hospitalization for persistent or worsening pneumonia that occurs after randomization and receipt of at least one dose of study drug.

- Persistent or worsening pneumonia is defined as receipt of a non-study systemic antibiotic for pneumonia or treatment for a complication of pneumonia, including drainage of pleural fluid, placement of a chest tube, video assisted thoracoscopic surgery, or thoracotomy procedures.
- Note: Receipt of a non-study antibiotic will not be regarded as satisfying this definition if it is related to a new diagnosis that is unrelated to the prior diagnosis of pneumonia.

²Resolution of symptoms is defined as the absence of all of the following:

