Randomization: Enrolled subjects will be randomized to short vs. standard course therapy at a 1:1 ratio, with stratification by 1) age group (<24 months vs. 24-71 months), 2) initially prescribed antibiotic (amoxicillin vs. amoxicillin-clavulanate vs. cefdinir), and 3) treatment site (emergency department vs. outpatient clinic/urgent care facility).

Intervention: Subjects will continue on the initially prescribed antibiotic through Day -1, until they have completed 5 days (i.e., 5 scheduled doses of once daily medication, 10 scheduled doses of twice daily medication) of antibiotic therapy [e.g., if a subject takes the first dose of antibiotic in the afternoon of Day -5, the first dose of study agent would occur on the afternoon of Day 1, providing 10 total scheduled doses of a twice daily prescribed antimicrobial]. The first day of receipt of study agent will be Day 1. Subjects assigned to standard course therapy will receive 5 additional days (10 doses) of the same initially prescribed antibiotic, with standardized twice-daily dosing. Subjects assigned to short course therapy will receive 5 more days (10 doses) of a matching placebo. Both the study agent and placebo may appear different than the commercial formulation the child originally received. The placebo will appear indistinguishable in

color, taste, thickness, and consistency as the active antibiotic the child would otherwise receive in the study. The study product will be labeled with a numerical code that masks site investigators, site staff, parent(s)/guardian(s) and children to the formulation.

Follow-up and Assessment of Endpoints: Subjects will be scheduled for the following assessment visits:

Visit 2: Outcome Assessment Visit #1, Day 6 to 10 (1-5 days after completing the study agent). Subjects will be evaluated for the components of the composite overall outcome, which include the adequacy of the subject's clinical response; persistence of symptoms of fever, tachypnea, or cough; the occurrence of any solicited events; and the duration of antibiotic therapy (both study product/placebo and any additional oral or parenteral antibiotic therapy prescribed by study or non-study providers).

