- Oral, rectal, axillary, or tympanic temperature $\geq 38.3^{\circ}\text{C}$ (100.9°F), confirmed by repeat measurement after at least 15 minutes, in the 24 hours preceding the Outcome Assessment Visit, unless attributed to a new process that is unrelated to the prior diagnosis of pneumonia;

- Elevated respiratory rate (RR >50 breaths/minute for children <24 months of age and >40 breaths/minute for children 24-71 months of age) at the time of the Outcome Assessment Visit;

- Presence of cough grade 2 or 3 at the Outcome Assessment Visit, defined as Grade 0 (no cough), Grade 1 (Occasional coughing [less than 4 times hourly]), Grade 2 (frequent coughing [4 or more times an hour], interferes with sleep), Grade 3 (almost constant coughing (never free of cough), makes sleep nearly impossible);

³ Solicited events will be captured daily until Outcome Assessment Visit #2; thereafter, parents/legal guardians will report symptoms based on memory aid and medical interview by study staff. For those with multiple solicited events, the ordinal response table will be based upon the most severe solicited event.

Day 1: Day 1 begins at the time the first dose of study product is administered and ends at 11:59 PM of that same day. If a subject has no recorded receipt of study product at the time of the analysis, then Day 1 will be defined as the date 5 days after the date of initiation of the initial antibiotic.

DOOR at Outcome Assessment Visit #1: Defined as above, using DOOR components from the following Study Days.

Adequate Clinical Response: Day 1 – Day 5

Resolution of Symptoms:

- o Fever as measured in the 24 hours prior to Outcome Assessment Visit #1. If a subject has a fever according to a single measurement, but no repeat measurement after at least 15 minutes has been performed, the subject will be analyzed as having a fever. If a subject has a fever according to the measurement taken as a part of vital signs

during Outcome Assessment Visit #1, the subject will be analyzed as having a fever at Outcome Assessment Visit #1. If the vital signs measurement shows no fever, and the parental assessment of fever during the previous 24 hours is missing, then fever will be treated as missing.

- o Respiratory Rate and Cough: determined at Outcome Assessment Visit #1

Solicited Events: Day 1 – Day 5

Number of Days of Antibiotic Use: Day 1 – Day 5

DOOR at Outcome Assessment Visit #2: Defined as above, using DOOR components from the following Study Days.

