study systemic antibiotic for pneumonia), or for which MAVPLEUR, MAVCHTB, MAVVIDEO, MAVTHOR, or MAVSURG were YES (treatment for a complication of pneumonia, including drainage of pleural fluid, placement of a chest tube, video assisted thoracoscopic surgery, or thoracotomy procedures), then the subject did not have adequate clinical response at OAV#1. If the subject had a MAV from Day 1 to Day 5 for which MAVHOSP and MAVHPPN were both YES (subject was hospitalized for the treatment of pneumonia or pneumonia complications), then the subject did not have adequate clinical response at OAV#1. Otherwise, if the subject had a MAV from Day 1 to Day 5 and either MAVABRX was missing, MAVABRX was YES and MAVABCP was missing, or any of MAVPLEUR, MAVCHTB, MAVVIDEO, MAVTHOR, or MAVSURG were missing, then adequate clinical response at OAV#1 is missing. Otherwise, if a subject has one or more MAVs from Day 1 to Day 5, with no MAV indicating receipt of a non-study systemic antibiotic for pneumonia or treatment for a complication of pneumonia, including drainage of pleural fluid, placement of a chest tube, video assisted thoracoscopic surgery, or thoracotomy procedures and no hospitalization for treatment of pneumonia or pneumonia complications and no MAV missing data as described, then the subject has adequate clinical response at OAV#1. Note that for determining whether the medical treatment or hospitalization falls within the period of Day 1 to Day 5, the date of the initial MAV will be used (MAVVISDT), rather than specific dates of surgery or hospitalization entered on the MAV form.

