If a subject has OAV#2 and did not have a medically attended visit (MAV) from Day 1 to Day 18, inclusive, then the subject had adequate clinical response for OAV#2. If the subject had a MAV from Day 1 to Day 18 for which MAVABRX and MAVABCP were both YES (receipt of a non-study systemic antibiotic for pneumonia), or for which MAVPLEUR, MAVCHTB, MAVVIDEO, MAVTHOR, or MAVSURG were YES (treatment for a complication of pneumonia, including drainage of pleural fluid, placement of a chest tube, video assisted thoracoscopic surgery, or thoracotomy procedures), then the subject did not have adequate clinical response at OAV#2. If the subject had a MAV from Day 1 to Day 18 for which MAVHOSP and MAVHPPN were both YES (subject was hospitalized for the treatment of pneumonia or pneumonia complications), then the subject did not have adequate clinical response at OAV#2. Otherwise, if the subject had a MAV from Day 1 to Day 18 and either MAVABRX was missing, MAVABRX was YES and MAVABCP was missing, or any of MAVPLEUR, MAVCHTB, MAVVIDEO, MAVTHOR, or MAVSURG were missing, then adequate clinical response at OAV#2 is missing. Otherwise, if a subject has one or more MAVs from Day 1 to Day 18, with no MAV indicating receipt of a non-study systemic antibiotic for pneumonia or treatment for a complication of pneumonia, including drainage of pleural fluid, placement of a chest tube, video assisted thoracoscopic surgery, or thoracotomy procedures and no hospitalization for treatment of pneumonia or pneumonia complications and no MAV missing data as described, then the subject has adequate clinical response at OAV#2. Note that for determining whether the medical treatment or hospitalization falls within the period of Day 1 to Day 18, the date of the initial MAV will be used (MAVVISDT), rather than specific dates of surgery or hospitalization entered on the MAV form.

The below pseudocode summarizes the logic for defining ACR at OAV#1.

```
if no recorded receipt of study product then ACR_OAV1=missing  
else if death then ACR_OAV1=NO
```

```

else if subject does not have OAV#1 then ACR_OAV1=missing
else if subject has no MAV from Day 1 to Day 5 then ACR_OAV1=YES
else if subject has one or more MAVs from Day 1 to Day 5 with
    (MAVABRX=YES and MAVABCP=YES) or
    MAVPLEUR=YES or
    MAVCHTB=YES or
    MAVVIDEO=YES or
    MAVTHOR=YES or
    MAVSURG=YES or
    (MAVHOSP=YES and MAVHPPN=YES)
    then ACR_OAV1=NO
else if subject has MAV from Day 1 to Day 5 with
    MAVABRX=missing or

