6.5.5. Ordinal Clinical Response at OAV#1 or OAV#2

If the subject died at any point of study participation, then OCR at OAV#1 will be 8.

Else if the subject has missing ACR at OAV#1 then OCR at OAV#1 will be missing.

Else if the subject did not have ACR at OAV#1 and was hospitalized from Day 1 to Day 5 then OCR at OAV#1 will be 7.

Else if the subject did not have ACR at OAV#1 and was not hospitalized from Day 1 to Day 5 then OCR at OAV#1 will be 6.

Else if the subject has missing resolution of symptoms at OAV#1 then OCR at OAV#1 will be missing.

Else if the subject did not have resolution of symptoms at OAV#1 then OCR at OAV#1 will be 5.

Else if the subject has missing most severe solicited event at OAV#1 then OCR at OAV#1 will be missing.

Else if the subject had a most severe solicited event of grade 3 at OAV#1 then OCR at OAV#1 will be 4.

Else if the subject had a most severe solicited event of grade 2 at OAV#1 then OCR at OAV#1 will be 3.

Else if the subject had a most severe solicited event of grade 1 at OAV#1 then OCR at OAV#1 will be 2.

Else OCR at OAV#1 will be 1.

If the subject died at any point of study participation, then OCR at OAV#2 will be 8.

Else if the subject has missing ACR at OAV#2 then OCR at OAV#2 will be missing.

Else if the subject did not have ACR at OAV#2 and was hospitalized from Day 1 to Day 18 then OCR at OAV#2 will be 7.

Else if the subject did not have ACR at OAV#2 and was not hospitalized from Day 1 to Day 18 then OCR at OAV#2 will be 6.

Else if the subject has missing resolution of symptoms at OAV#2 then OCR at OAV#2 will be missing.

Else if the subject did not have resolution of symptoms at OAV#2 then OCR at OAV#2 will be 5.

Else if the subject has missing most severe solicited event at OAV#2 then OCR at OAV#2 will be missing.

Else if the subject had a most severe solicited event of grade 3 at OAV#2 then OCR at OAV#2 will be 4.

Else if the subject had a most severe solicited event of grade 2 at OAV#2 then OCR at OAV#2 will be 3.

Else if the subject had a most severe solicited event of grade 1 at OAV#2 then OCR at OAV#2 will be 2.

Else OCR at OAV#2 will be 1.

Note that in some cases OCR can be defined even if some components are missing. For instance, if a subject had record of receipt of study product and did not have adequate clinical response at OAV#1, OCR at OAV#1 would still be defined even if most severe solicited event at OAV#1 was missing.

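### The Visit #1 DOOR counts pneumonia failures and antibiotic days only to Day 5 but scores symptoms at the Day 6-10 visit, so a failure first attended in between can rank as a resolved case, and no sensitivity analysis tests this

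*Protocol*

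**What the plan says.** **The window.** Protocol section 11 states that "DOOR at Outcome Assessment Visit #1 is computed using data from Day 1 to Day 5". SAP 3.3 sets "Adequate Clinical Response: Day 1 – Day 5" and gives solicited events and days of antibiotic use the same limits. The SAP 6.5.1 pseudocode reads "else if subject has no MAV from Day 1 to Day 5 then ACR_OAV1=YES". For rank 7, SAP 6.5.5 requires both conditions, in the line that begins "Else if the subject did not have ACR at OAV#1 and was hospitalized from Day 1 to Day 5 then OCR at OAV#1 will be". SAP 6.5.6 drops systemic antibiotic days outside the window.

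**What is measured later.** SAP 3.3 has "Respiratory Rate and Cough: determined at Outcome Assessment Visit #1", and fever covers the 24 hours before that visit. Protocol section 4 places the visit after the window has closed: "Visit 2: Outcome Assessment Visit #1, Day 6 to 10 (1-5 days after completing the study agent". Death at any time in the study is rank 8 (SAP 6.5.5).

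**Text with no Day 5 limit.** Protocol 3.2.1, Table 1 footnote 1, counts a qualifying event "that occurs after randomization and receipt of at least one dose of study drug". Protocol section 4 speaks of inadequate response identified before Outcome Assessment Visit #1. Protocol 9.5.2 treats any need for off-study antimicrobial therapy as inadequate response, and the Visit #1 procedures in 7.3 collect events up to the visit.

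**The concern.** The two halves of the score refer to different times. Rescue treatment started after Day 5 escapes the failure count, and it may also clear the symptoms read at the visit. Such a child can then sit among the best outcomes of the trial.

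The same derivation feeds the primary test, the interim efficacy test (SAP 6.6) and the Visit #1 non-inferiority test of the ordinal clinical response against 0.40 (SAP 8.2.6.1). Under standard therapy, study drug is scheduled through Day 5, so a failure attended after that therapy ends falls outside the Visit #1 failure window.

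**Working it through.** **1. The plan's own figure.** The Noether formula in SAP section 5 gives N = (1.960 + 1.282)² / [12 × 0.25 × 0.10²] = 350.2, against 360 stated. Power at 360 is 0.908. The formula uses only the assumed probability, so the window does not affect it. The documents give no figure for Day 6-10 events.

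**2. Length of the gap.** With a Day 6 visit, the uncovered time is part of one day. With a Day 10 visit, it is Days 6 to 9 (four full days) plus part of Day 10.

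**3. Scoring test children.** SAP 6.5.7 defines score = ordinal rank + antibiotic days / 100, lower being better. Take a Day 10 visit, symptoms resolved, no solicited events on Days 1-5, full adherence, and rescue antibiotic from the day of first attendance through the visit:

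| First attended | SAP rules, short / standard | Counted to the visit, short / standard |
|---|---|---|
| Day 5, clinic | 6.01 / 6.05 | 6.06 / 6.10 |
| Day 5, hospitalized | 7.01 / 7.05 | 7.06 / 7.10 |
| Day 7, clinic | 1.00 / 1.05 | 6.04 / 6.09 |
| Day 7, hospitalized | 1.00 / 1.05 | 7.04 / 7.09 |
| Day 9, hospitalized | 1.00 / 1.05 | 7.02 / 7.07 |

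For the Day 7 admission in the short arm, the SAP gives 1 + 0/100 = 1.00, the best possible score. Counted to the visit, the antibiotic days are Days 7 to 10, so 7 + 4/100 = 7.04.

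**4. Effect on the indices (assumed inputs).** Assume ranks 1 to 7 at 55/25/8/2/9/0.8/0.2% in both arms, with 0 antibiotic days in the short arm and 5 in the standard arm. The ordinal index is 0.500. All ties in rank go to the short arm, so Pr(higher DOOR) = 0.5 + 0.5 × Σp² = 0.5 + 0.5 × 0.380 = 0.690.

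Move a fraction L of ranks 1-5 (99% of the arm), pro rata, to rank 6, leaving antibiotic days unchanged.
- Short arm, ordinal index: change = −L × (0.49995 − 0.99 × 0.006) = −0.494L, or 0.0049 per 1%.
- Short arm, DOOR: change = −L × (0.6899 − 0.99 × 0.010) = −0.680L, or 0.0068 per 1%.
- Standard arm: the ordinal index rises by 0.494L. DOOR rises by L × (0.99 × 0.998 − 0.680) = 0.308L, or 0.003 per 1%.

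Taking the short-arm children only from ranks 1-4 gives similar values per 1%: 0.01 × (0.495/0.90 − 0.006) = 0.0054 and 0.01 × (0.6809/0.90 − 0.010) = 0.0075.

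| Late failure, short / standard | Pr(higher DOOR) | Ordinal index |
|---|---|---|
| Any, SAP rules | 0.690 | 0.500 |
| 1% / 1%, counted | 0.686 | 0.500 |
| 2% / 0%, counted | 0.676 | 0.490 |
| 5% / 0%, counted | 0.656 | 0.475 |
| 10% / 0%, counted | 0.622 | 0.451 |
| 0% / 5%, counted | 0.705 | 0.525 |

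**5. Against the 0.40 bound.** With 180 per arm and the untied variance in the footnote to SAP Table 16, the 95% half-width is 1.96 × √[361 / (12 × 180 × 180)] = 0.060. The lower limits are then about 0.430, 0.415 and 0.391 for ordinal indices of 0.490, 0.475 and 0.451. Of these cases, only 10% against 0% falls below 0.40.

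**The case against.** The common window is deliberate and disclosed. Protocol section 11 states it, SAP 2.1 describes outcomes from the first five study days together with those at the visit, and the derivations apply it consistently. It gives every child the same time at risk although visits fall anywhere in Day 6-10. Footnote 1 to Table 1 fixes a start point and no end point, so it does not by itself require counting to the visit. All of this stands, and it is why the primary test should not change.

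The late failures are also reported elsewhere. The Visit #2 DOOR and ordinal response count them over Day 1-18, Tables 28-29 compare them by arm, Table 57 shows Day 6-18 separately, and Listings 13-14 give the study day of each visit. The footnote to Table 14 asks for review of components and sensitivity analyses before any conclusion. This also stands, but it leaves a gap. Table 57 pools Day 6-18, so it does not isolate events before Visit #1. The complete-case, according-to-protocol, worst-case and tie-break-threshold analyses all keep the same Visit #1 derivation.

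A reader might infer that any child rescued or hospitalized before the visit can score as a success. The rules do not support that. Events first attended on Days 1-5 count. A Day 5 attendance leading to a later admission also counts, because "the date of the initial MAV will be used (MAVVISDT), rather than specific dates of surgery or hospitalization entered on the MAV form". A child still symptomatic at the visit is rank 5, and a child with no Visit #1 has a missing response and is imputed.

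**Conclusion.** The mechanism is certain from the SAP text, and its effect is unknown. A failure first attended from Day 6 up to Visit #1, with symptoms resolved by then, is scored 1 to 4, and its antibiotic is not counted.

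Three stronger readings are not supported:
- That half of the time before the visit is ignored. The gap is at most four full days plus part of the visit day.
- That relapse after stopping can be seen in the short arm only. This is so for attended failures in the Visit #1 window, but visit symptoms are read after study agent ends in both arms, and the Day 1-18 analyses cover both.
- That the primary result is biased towards short course. Over Days 1-5 the short arm is off antibiotic and the standard arm is on it, so the cut-off could hide late failures in either arm.

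Under the assumed mix, DOOR superiority would survive even 10% against 0% late failure (0.622, power 0.98 at N = 360). The ordinal non-inferiority result is more exposed. These sizes rest on the assumed rank mix, full adherence and every late failure having resolved by the visit. The point is a worthwhile, inexpensive robustness check and does not invalidate the primary analysis.

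**What to change.** Keep the Day 1-5 window for the primary test. Reconcile Protocol 3.2.1 (Table 1 footnote 1), Protocol section 11 and SAP 3.3, so that each states which components stop at Day 5, which are read at the visit, and that death is counted throughout.

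In SAP 8.2.2 and 8.2.6, pre-specify one sensitivity analysis of the Visit #1 DOOR and ordinal response in which failures and antibiotic days count through the actual Visit #1 date. Report the number of children reclassified in each arm.

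The cost is one extra derivation and its tables, using attendance and concomitant-medication dates already collected. Sample size is unaffected. The drawback is that follow-up then varies with visit day (6 to 10), so this should remain a sensitivity analysis.
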